##### 3. Pruritus Numeric Rating Scale (NRS)

The NRS for pruritus is an assessment tool that will be used to assess the patient's worst itch as a result of their AD in the previous 24 hours. This will be recorded daily, ideally in the morning, using an internet-enabled device with patients asked, "On a scale of "0" (no itch) to "10" (worst imaginable itch), how was your worst itch in the past 24 hours?". Patients will additionally be asked to record NRS for 7 consecutive days immediately prior to Baseline. Sites will be encouraged to contact patients who have missed 2 consecutive e-diary entries to encourage patient compliance.

The baseline for weekly average pruritus NRS score is defined as the average of daily non-missing scores obtained during the 7 days prior to randomization (Day -6 to Day 1). A minimum of 4 daily scores out of the 7 days is required to calculate the baseline average score. The post-baseline weekly average pruritus NRS score is calculated as the average of daily non-missing scores obtained from the reported daily NRS within the week up to and including target day of the scheduled visit.

#### 4. SCORing of Atopic Dermatitis Index

The SCORAD Index is a validated clinical tool developed to standardise the evaluation of the extent and severity of AD [SCORAD Dermatol Basel Switz 1993]. This assessment will be completed using an internet-enabled device. To determine the extent of AD, the affected area (A) as a percentage of the whole body is determined, with a maximum score of 100% (head and neck [9%], upper limbs [9% each], lower limbs [18% each], anterior trunk [18%], back [18%], genitals [1%]). The severity (B) of 6 specific symptoms of AD (redness, swelling, oozing/crusting, scratch marks, skin thickening [lichenification], dryness [area where there is no inflammation]) is assessed on a 4 point scale, with a maximum score of 18: none (0), mild (1), moderate (2) or severe (3). Patientive symptoms (ie, itch and sleeplessness; C) are recorded as scored by the patient or relative on a visual analogue scale (VAS), where 0 is no itch (or sleeplessness) and 10 is the worst imaginable itch (or sleeplessness), with a maximum possible score of 20.

The SCORAD score for each patient is calculated as:  $A/5 + 7B/2 + C$ .

#### 5. Body Surface Area Involvement of Atopic Dermatitis

Body surface area (BSA) affected by AD will be assessed for each section of the body (the possible highest score for each region is: head and neck [9%], anterior trunk [18%], back [18%], upper limbs [18%], lower limbs [36%], and genitals [1%]) and will be reported as a percentage of all major body sections combined.

#### 6. Patient Oriented Eczema Measure

The POEM is a tool used for monitoring atopic eczema severity. It focuses on the illness as experienced by the patient. This will be completed using an internet enabled device.

The questionnaire consists of 7 questions pertaining to the symptoms of AD and their frequency. Scores are based on a scale of zero (no days) to 4 (every day in the last week) for each question, with a maximum score of 28 possible for all questions. A POEM total score is correlated to eczema severity (0 2 [clear or almost clear], 3 7 [mild], 8 16 [moderate], 17 24 [severe], 25 28 [very severe]).

#### 7. Dermatology Life Quality Index

The DLQI is a dermatology specific QoL instrument and is a simple, validated questionnaire. This will be completed using an internet enabled device.

The instrument consists of 10 questions pertaining to the effect of AD on QoL. Scores are based on a scale of "0" (not at all/not relevant/question unanswered) to "3" (very much/prevented work

or studying), with a maximum score of 30 possible for all questions. The total score is correlated to the detrimental effect of AD on QoL (0 1 [no effect at all on patient's life], 2 5 [small effect], 6 10 [moderate effect], 11 20 [very large effect] and 21 30 [extremely large effect]).

#### 8. Atopic Dermatitis Control Tool

The ADCT is a validated 6-item instrument with a 7-day recall period to measure AD disease control. This will be completed using an internet enabled device. The following domains are assessed: overall severity of symptoms, frequency of intense episodes of itching, severity of bother of itching, frequency of sleep impact, severity of daily activities impact, severity of mood or emotions impact. Each item is scored from 0 (none) to 4 (extreme). A total score of 7 or more points (derived by adding item scores) was identified during validation as an optimum threshold to identify patients whose AD is "not in control".

#### 9. Hospital Anxiety and Depression Scale

The HADS is a validated 14-item PRO measure used to assess states of anxiety and depression over the past week. This will be completed using an internet enabled device. Only the HADS total score will be presented in the analysis

## 5. Patient Disposition

### 5.1 Disposition

Patient disposition will be summarized by study treatment group and overall.

Disposition of patients includes the counts and percentages of patients for the following categories: screened, screen failures, randomized, patients who completed the study treatment, patients who discontinued from the study treatment, patients who completed the study, patients who discontinued from the study, patients who completed Week 24, patients re-randomised at Week 24, number of patients who enter in LTE, patients who discontinued from study treatment prior to Week 24, patients who discontinued from study prior to Week 24, and patients who provide consent for the skin biopsy sub-study. For patients who discontinue treatment prior to week 24 or discontinue study prior week 24, the denominator will be the number of patients randomized for part 1. For screened and screen failure, only the total count will be provided.

Similar disposition items will be summarized for Part 2, treatment completion, early discontinuation from treatment, study completion, early discontinuation from study, etc. The denominator for Part 2 disposition table will be the number of patients that were re-randomized at Week 24.

The primary reasons for study and treatment discontinuation will be also provided.

Study analysis population will be summarized for Part 1 by Part 1 randomization arms; for Part 2 by Week 24 re-randomization treatment arms.

Any discontinuation due to COVID-19 will also be summarized.

Patient disposition and discontinuation data will be presented in a listing.

## 5.2 Protocol Deviations

Deviations from the protocol will be recorded in clinical trial management system (CTMS).

Significant/non-significant protocol deviations will be presented in a summary table using counts and percentages by protocol deviation category for the FAS. All protocol deviations will be listed with date of occurrence, deviation category and deviation description.

All protocol deviations from COVID-19 positive patients will be listed with date of occurrence, deviation category and deviation description separately.

## 5.3 Inclusion and Exclusion Criteria

The details of Inclusion and Exclusion criteria are listed in Section 4.2 and 4.3 of the protocol. For patients who did not satisfy these criteria, the inclusion and exclusion criteria will be listed with the deviation.

## 6. Demographics and Baseline Characteristics

### 6.1 Demographics

The analysis will be based on the FAS1 & FAS2 and the SAF1 & SAF2 for Part 1 and Part 2, respectively.

The demographics and baseline characteristics will be presented in tables using descriptive statistics. The demographic characteristics consist of age (Years), sex, race, ethnicity. The baseline characteristics consist of height (cm), weight (kg) and body mass index (BMI [kg/m^2]), disease severity, region, EASI score (IRT and eCRF data), IGA, pruritus NRS, BSA, SCORAD, POEM, DLQI, HADS, ADCT collected at baseline. Descriptive statistics (n, mean, standard deviation, median, minimum, and maximum) for age, height, weight and BMI at baseline will be calculated overall and by treatment group. The counts and percentages of patients by sex (male, female), ethnicity, race, disease severity (moderate/severe) and region will be calculated overall and by treatment group. Percentages will be based on the total number of patients in each treatment group.

Patient demographic and baseline characteristics will be presented in a listing.

### 6.2 Medical History

#### 6.2.1 General Medical History

Medical history will be coded using the latest version of Medical Dictionary for Regulatory Activities (MedDRA) Version 22.0 or later.

The data for medical history will be summarized with counts and percentages of patients overall and by treatment group. Patient general medical history data including specific details will be presented in a listing. The analysis will be based on the FAS1 and the SAF1 for Part 1 and FAS2 for Part 2.

### 6.2.2 Disease-Specific History

Duration of AD calculated as time from onset to randomization, disease severity at baseline as determined by EASI and IGA at baseline (both per IRT and eCOA) will be presented in demography and baseline characteristics outputs.

## 7. Treatments and Medications

### 7.1. Prior and Concomitant Medications

All medications/vaccinations will be coded according to the World Health Organization drug dictionary (WHODRUG Global B3 March 2021 or later).

Prior medications refer to medications that started any time prior to first dose of study treatment or randomization if that is not available regardless of the end date. AD treatments include systemic and non-systemic corticosteroids, systemic and non-systemic calcineurin inhibitors, and systemic and non-systemic treatment for AD or other indications with an immunosuppressive/immunomodulating substance including (but not limited to) dupilumab, JAKi and aIL13 mABs. Treatments given to AD will be collectively analyzed from all applicable eCRF pages: Concomitant Medications, Prior and Current Systemic and Topical Treatments for AD.

Concomitant medications refer to medications started prior to AND continued after the first dose of study treatment or taken any time after the first dose of study treatment up to the follow-up visit.

The prior and concomitant medications will be summarized separately. At each level of summarization, a patient is counted once if he/she reports one or more medications at that level. Drug class will correspond to the Anatomical Therapeutic Classification (ATC) Level 4 term or other AD-specific, WHODRUG-based classification.

All prior medications will be summarized using counts and percentages.

All concomitant medications will be summarized using counts and percentages for the FAS1 and FAS2 for Part1 study and Part 2 study respectively.

The imputation algorithm for partial and missing medication dates is provided in Appendix 15.2.

All prior and concomitant medications will be presented in a listing.

### 7.2. Permitted Concomitant Medications

Other than the prohibited medications listed in Section 7.3, treatment with concomitant medication is permitted during the study. This includes treatment with oral contraceptives, nasal, otological, intraarticular and inhaled corticosteroids for any duration, and oral or topical antibiotics for up to 2 weeks for AD-associated superficial skin infections.

### 7.3. Prohibited Concomitant Medications (and Procedures)

Treatment with the following concomitant medications is prohibited during the study:

- Dupilumab.
- Topical or systemic tacrolimus and pimecrolimus (exceptions might apply per protocol).
- Topical or systemic corticosteroids (exceptions might apply per protocol, e.g. topical steroids used for rescue purpose).
- Leukotriene inhibitors.
- Allergen immunotherapy.
- Systemic treatment with an immunosuppressive/immunomodulating substance (including, but not limited to aIL13 mABs, JAKi, aOX40 mAbs, cyclosporine, mycophenolate-mofetil, IFN- $\gamma$ , azathioprine, methotrexate, or biologics).
- [REDACTED]

The following concomitant procedures are prohibited during study participation:

- Elective surgical procedures.
- Ultraviolet (UV) procedures (phototherapy [narrowband UVB, UVB, UVA1 or psoralen UVA]).
- Tanning in a booth/parlour.
- More than 2 bleach baths per week.

#### 7.4. Rescue Medications

AD rescue therapy is not permitted in the first 14 days following randomisation. Any AD rescue therapy administration either topical or systemic during this period will result in permanent discontinuation from the IMP. Bland emollients are not considered rescue therapy for AD, and should be maintained during this period as per protocol.

If medically unavoidable after Day 14 (ie, to control intolerable AD symptoms), rescue treatment for AD may be provided to study patients at the discretion of the Investigator. For the purpose of efficacy analysis, patients who receive rescue topical treatment during this study treatment period will be considered treatment failures but can continue study treatment if the rescue treatment consists of topical medications only.

If topical corticosteroids (TCS) are needed, it is recommended that the investigator start with the least potent TCS for the face (eg, hydrocortisone 2.5% cream/ointment) and moderately potent TCS for the body (eg, triamcinolone acetonide 0.1% cream/ointment), applied up to twice daily. Where the use of moderate potency topical corticosteroids (TCS) is not considered clinically appropriate, low potency TCS or topical calcineurin inhibitors can be used, however, these should be reserved for problem areas only. Topical PDE4 inhibitors are also permitted.

Patients should use topical rescue therapy only for as long as necessary to control problem areas on a maximum of 2 occasions during study participation, and for a maximum of 2 consecutive weeks on each occasion.

If a patient receives rescue treatment with high potency TCS, systemic corticosteroids or non-steroidal systemic immunosuppressive drugs (cyclosporine, methotrexate, mycophenolate mofetil, azathioprine, etc) or receives more than 2 episodes of topical rescue treatment, study treatment will be immediately discontinued.

Investigators should conduct efficacy and safety assessments immediately before administering any rescue treatment. An unscheduled visit may be required.

All patients should complete the schedule of study visits and assessments whether or not they complete study treatment and whether or not they receive rescue treatment for AD. If a patient has IMP permanently discontinued due to the taking of systemic therapy rescue but consent is retained, study assessments may be continued until Day 169 (Week 24) for patients who discontinue IMP in the first study period, or until Day 365 (Week 52) or the end of the safety follow-up period (whichever is longer) in patients who discontinue IMP after Day 169 (Week 24).

Rescue medication will be coded according to the World Health Organization drug dictionary (Global B3 March 2021 or later). Drug class will correspond to the Anatomical Therapeutic Classification (ATC) Level 4 term or other AD-specific, WHODRUG-based classification. The data will be summarized using counts and percentages by preferred drug name for each treatment group and overall. At each level of summarization, a patient is counted once if the patient reported more than one medication. The analysis will be based on FAS1 & FAS2 for Part 1 and Part 2, respectively.

A listing of rescue medications will be presented.

A blinded medical review of rescue/prohibited treatments will be implemented before or at the time of each database lock by considering the type of medication, indication, timing, frequency and the potential impact of the use of the prohibited medication or procedure on efficacy.

Categorization of medications performed within the frame of this review will be the basis of related intercurrent event determination in line with the estimand strategy in Section 8.

## 7.5 Study Treatments

### 7.5.1 Extent of Exposure

Drug exposure is defined as the total number of weeks + 28 days a patient is exposed to study treatment. Duration of exposure (weeks) in Part 1 is derived as (Last dose date in Part 1 - First dose date in Part 1 + 1)/7 + 4 weeks. Duration of exposure (weeks) in Part 2 is derived as (Last dose date in Part 2 - First dose date in Part 2 + 1)/7 + 4 weeks. The duration of exposure and dose will be summarized in a table by treatment group and overall, using descriptive statistics (n, mean, standard deviation, median, minimum, and maximum). The number and percentages of patients

for the cumulative duration of exposure will be presented for below categories:  $\geq 4$  weeks,  $\geq 8$  weeks,  $\geq 12$  weeks,  $\geq 16$  weeks,  $\geq 20$  weeks,  $\geq 24$  weeks (and  $\geq 28$  weeks for Part 2 study only). Study treatment administrations will be summarized and listed by treatment group in the main period and transition.

The analysis will be based on SAF1 & SAF2 for Part 1 and Part 2, respectively.

### **7.5.2 Treatment Compliance and Modifications**

The overall compliance by treatment group will be summarized descriptively. For each patient, the compliance will be calculated as the total amount of actual drug administered divided by the expected number of drug administered which is 2 injections per subject at baseline followed by 1 injection Q4W onwards.

The compliances will then be classified into one of the following categories:  $<80\%$ ,  $80\% - <100\%$ , and  $\geq 100\%$  and will be presented as the number and percentage of patients in each category. Descriptive statistics will be provided for overall compliance, for each treatment group. Percentages will be computed using the number of patients in each treatment group. A summary of each patient's compliance will be presented in a listing.

The analysis will be based on SAF1 & SAF2 for Part 1 and Part 2, respectively.

[figure not shown]
## **8. Efficacy Analysis**

[figure not shown]
### **8.1 Analysis of Primary Efficacy Endpoint**

[figure not shown]
The primary efficacy endpoint is the percentage change in EASI from baseline to Day 113 (Week 16).

The primary analysis will be conducted on the FAS1 after all randomized patients have reached the Day 169 (Week 24) visit/early termination.

[figure not shown]
### **Table 3 Estimands and Strategies for Managing Intercurrent Events for Primary Endpoint**

Multiple imputation will be performed using the imputation method described in the tipping point analysis section given below (Steps 1, 2 and 5).

### **Tipping point analysis**

, a tipping point analysis will be performed for the primary endpoint with imputed missing Week 16 values as follows:

- Step 1. Monotone missing pattern will be induced by Markov Chain Monte Carlo (MCMC) method using PROC MI, with seed=293874: for patients who have intermediate missing values, the intermediate missing values will be imputed assuming a multivariate normal distribution over observations from all visits. 40 datasets with a monotone missing pattern will be obtained using this method.
- Step 2. For each of the imputed dataset with monotone missing pattern obtained in Step 1, the remaining missing data will be imputed using the regression method for the monotone- pattern, with seed=293874 with adjustment for covariates including response variable, intervention groups, randomisation strata (region, disease severity), and baseline value of the corresponding endpoint. All available data in the monotone missing pattern data will be used. One imputed dataset will be obtained for each of the imputed dataset at Step 1. So, 40 fully imputed datasets will be obtained altogether.
- Step 3. The imputed values in each KY1005 dose arm are added by a positive amount  $d$  for each imputed data set.
- Step 4. The imputed values in placebo group are subtracted by a positive amount  $p$  for

each imputed data set.

- Step 5. Change from baseline in endpoint will be analyzed using ANCOVA model same as the one in primary analysis. Then, the SAS MIANALYZE procedure will be used to generate statistical inferences by combining results from the 40 analyses using Rubin's formula.

Step 3 to Step 5 will be repeated iteratively until the p-value for treatment effect of each KY1005 dose arm compared to placebo estimated in Step 5 is  $>0.05$ .

Summary of EASI values, absolute and percent change from baseline values at scheduled visits will be provided. Line plots will be provided. Further details please refer to Section 8.3.

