10.4.2.1 Primary Analysis

The primary efficacy endpoint is the percentage change in EASI from Baseline to Day 113 (Week 16). This will be assessed using an ANCOVA model.

The primary analysis will be conducted on the FAS after all patients have reached the Day 169 (Week 24) visit/early termination.

Property of the Sanofi Group - strictly confidential

PAGE 106 OF 147

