#### Calculation of Change and Percent Change from Baseline

Change from Baseline to any trial Week t ( $C_t$ ) is calculated as follows:

$C_t = M_t - M_B$ , where:

- $M_t$  is the measurement of interest at Week t
- $M_B$  is the measurement of interest at Baseline

Percent change from Baseline to any trial Week t ( $P_t$ ) is calculated as follows:

$$P_t = 100*(C_t/M_B)$$

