### **Analysis for continuous key secondary endpoint**

Below Estimands will be applied to analyze the continuous key secondary endpoint: Percentage change from baseline in EASI at Day 169 (Week 24). Please refer the details in Section 15.1 in Appendices. For analysis approach with multiple imputation, same multiple imputation process described for primary endpoint will be applied for the continuous key secondary endpoint.

- Estimand 4a description: The mean difference in percentage change from baseline in EASI to Day 169 (Week 24) of 4 different KY1005 dosing regimens compared to placebo, [REDACTED] in adult patients with moderate to severe AD who have had inadequate response to topical treatments or inadvisability of topical treatment.

The analysis of the key secondary endpoint and the handling of intercurrent events and missing data will be performed similar to Estimand 1 (Table 3 Estimands and Strategies for Managing Intercurrent Events for Primary Endpoint **Table 3**, Column 2).

- Estimand 4b description: The mean difference in percentage change from baseline in EASI to Day 169 (Week 24) of 4 different KY1005 dosing regimens compared to placebo, [REDACTED] in adult patients with moderate to severe AD who have had inadequate response to topical treatments or inadvisability of topical treatment.

The analysis of the key secondary endpoint and the handling of intercurrent events and missing data will be performed similar to Estimand 2 (Table 3 Estimands and Strategies for Managing Intercurrent Events for Primary Endpoint **Table 3**, Column 3).

[figure not shown]
- Estimand 4c description: The mean difference in percentage change from baseline in EASI to Day 169 (Week 24) of 4 different KY1005 dosing regimens compared to placebo, [REDACTED] in adult patients with moderate to severe AD who have had inadequate response to topical treatments or inadvisability of topical treatment.

[figure not shown]
The analysis of the key secondary endpoint and the handling of intercurrent events and missing data will be performed similar to Estimand 3 (Table 3 Estimands and Strategies for Managing Intercurrent Events for Primary Endpoint **Table 3**, Column 4).

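### Step 5 of the SAP's multiple-imputation and tipping-point procedure names change from baseline as the ANCOVA response, although the endpoints it serves are percentage change in EASI; probably a drafting slip, but it should be corrected.

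*SAP*

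**What the plan says.** SAP 8.1 sets the endpoint: "The primary efficacy endpoint is the percentage change in EASI from baseline to Day 113 (Week 16"). Protocol 10.4.2.1 says the same and assesses it with an ANCOVA. The continuous key secondary endpoint in SAP 8.2 is percentage change in EASI at Week 24.

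Under Tipping point analysis, the SAP announces that "a tipping point analysis will be performed for the primary endpoint with imputed missing Week 16 values as follows" and gives five steps:

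- Steps 1 and 2 impute the missing data, giving 40 completed datasets.
- Step 3 adds a positive amount d to the imputed values in each KY1005 arm.
- Step 4 subtracts a positive amount p from the imputed values in the placebo arm.
- Step 5 fits the model and pools with Rubin's rules. It names its response as follows: "Change from baseline in endpoint will be analyzed using ANCOVA model same as the one in primary analysis".

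Steps 3 to 5 are repeated until the p-value for each dose against placebo exceeds 0.05.

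The procedure is also used outside the tipping point. The sentence beneath Table 3 reads: "Multiple imputation will be performed using the imputation method described in the tipping point analysis section given below (Steps 1, 2 and 5"). For Week 24, SAP 8.2 says that the "same multiple imputation process described for primary endpoint will be applied for the continuous key secondary endpoint".

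SAP Section 4 gives separate formulas for "Change from Baseline to any trial Week t" (value minus baseline) and for "Percent change from Baseline to any trial Week t" (100 times that difference, divided by baseline).

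**The concern.** By the SAP's own definitions, Step 5 names a different variable from the endpoint it is meant to analyse. Elsewhere the SAP keeps the two apart. SAP 8.3 lists absolute change in EASI, including at Week 16, as a separate secondary endpoint. The closing lines of the tipping-point text mention absolute and percent change side by side.

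The response variable in Step 5 produces the pooled estimate and p-value of every analysis that runs through it. It also decides where the tipping-point search stops. A programmer who follows the sentence literally would report a treatment difference in EASI points, and a robustness check of that difference, under the label of the percentage-change endpoint.

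A related gap lies in Steps 3 and 4: d and p have no stated unit.

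**Working it through.** **1. Does the text settle the variable?**

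| Place | Variable named |
|---|---|
| Protocol 10.4.2.1; SAP 8.1 opening | Percentage change, Week 16 |
| SAP 8.2, endpoint and Estimands 4a to 4c | Percentage change, Week 24 |
| SAP 8.1, tipping-point lead-in | The primary endpoint |
| SAP 8.1, Step 2 covariates | A baseline value of the endpoint |
| SAP 8.1, Step 5 | Change from baseline |

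Percentage change has no baseline value of its own, so in Step 2 the word endpoint must stand for the EASI score. Carried into Step 5, that makes the response the change in EASI score, in points. The other rows point to percentage change. The visible text conflicts, and nothing visible says that Step 5 means percentage change.

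**2. Are the scales interchangeable?** With baseline B, Week 16 value M and change C = M − B, percentage change is P = 100·C/B, so C = P·B/100. The multiplier B differs between patients, so moving from P to C is not a change of units. It gives more weight to patients with high baselines, and the ANCOVA test statistic changes even with baseline as a covariate.

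Baselines: 16 is the entry minimum (Protocol 4.2), 21 the severity cut (SAP 3.1), 72 the EASI maximum, and 30 is illustrative.

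| Baseline B | 10-point fall, 100·10/B | Shift of 5 points, 100·5/B |
|---|---|---|
| 16 | 62.5% | 31.25 percentage points |
| 21 | 47.6% | 23.8 |
| 30 | 33.3% | 16.7 |
| 72 | 13.9% | 6.9 |

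The 5-point shift is my example; the visible SAP gives no values for d or p.

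**3. Could the choice change a conclusion?** This is an illustration on assumed inputs, not a figure from the plan.

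- Means at Week 16: −69.97 and −49.37 (Phase 2a high dose and placebo, Protocol Table 1-1).
- SD: 40. From the confidence intervals in that table, half-width/1.99 × √n gives 15.435/1.99 × √27 = 40.3, 15.07/1.99 × √27 = 39.3 and 16.65/1.99 × √24 = 41.0.
- 70 patients per arm, one active arm against placebo, 3,000 simulated trials per scenario, no missing data.
- Percentage change floored at −100 and capped so that EASI does not exceed 72. The floor pulls the mean difference below the nominal 20.6 points.
- ANCOVA on treatment, baseline and severity (above 21 or not); region omitted.
- Baseline: 16 plus a gamma variable, capped at 72, in two scenarios.

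| Baseline mean (SD parameter) | Mean effect, percentage change | Mean effect, EASI points | Power, percentage / absolute | Significance differs |
|---|---|---|---|---|
| 25 (8) | −17.3 | −4.3 | 83.1% / 79.5% | 7.7% of trials |
| 30 (12) | −17.1 | −5.1 | 83.6% / 78.9% | 9.5% of trials |

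**4. The plan's own figure.** The protocol synopsis states at least 84% power with 70 per arm. The effect size and SD behind it are not visible, so it cannot be reproduced. A two-sided t-test at 5% with 70 per arm reaches 84% at a standardised difference of 0.503. The point here does not depend on that figure.

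**The case against.** The strongest reply is that the context fixes the scale. The steps are introduced as an analysis of the primary endpoint. The model must match the primary ANCOVA, which Protocol 10.4.2.1 applies to percentage change. SAP 8.2 reuses the process for Estimands 4a to 4c, each defined as a mean difference in percentage change, and a model of EASI points cannot deliver that. When the SAP lists the points-scale endpoint it writes absolute change, so the bare word in Step 5 may be a generic sentence carried over. This stands as evidence of intent, and I take the wording to be a probable slip. It does not correct the sentence: the instruction to match the primary analysis describes the model, while the response is named separately.

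Three stronger readings are tempting, and the documents do not support them.

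- *The primary analysis itself will be run on the wrong scale.* The body of Table 3 and the opening of the tipping-point sentence are not shown. Which estimands use imputation, and whether a cell names the response, cannot be checked.
- *A tipping value in EASI points says nothing about a percentage-change result.* If d is added to the imputed Week 16 scores and percentage change is then computed, each imputed patient moves by 100·d/B percentage points. The d at which significance is lost is a valid tipping point for the percentage-change analysis.
- *The shifts must be in percentage points.* That is a preference. If the imputed values are EASI scores, as Step 2 suggests, EASI points are the natural reading; the SAP only needs to say so.

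It is also fair to say that the simulation replaces the response in complete data. It does not measure the effect of Step 5 on an imputation-based or tipping-point analysis.

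**Conclusion.** The inconsistency is real and limited. Step 5 names absolute change where the endpoints it serves are percentage change, and Section 4 treats these as different variables. Followed literally, the imputation-based analyses of the primary and Week 24 endpoints and the tipping-point p-value would be on the absolute scale. How much of the main result this touches is unknown from the visible text.

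The per-patient difference between the scales is arithmetic: a factor of 72/16 = 4.5 between the extremes of possible baseline. The 7.7% to 9.5% disagreement rests on assumed baselines, an assumed SD of 40 and no missing data. It shows only that the choice can matter. The missing unit for d and p is a smaller gap of the same kind.

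**What to change.** Reword Step 5 along these lines: *Percentage change from baseline in EASI, computed from the imputed values, will be analysed using the same ANCOVA model as in the primary analysis.*

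In Steps 3 and 4, state whether d and p are EASI points, applied to the imputed scores before percentage change is computed, or percentage points, applied afterwards. If Table 3 names a response variable, check that it agrees.

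The cost is a few sentences in the SAP, with no change to design or data collection.
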